7.2. Drug-Related Adverse Event

An adverse event that may be reasonably attributed, in the judgment of the Investigator, to the study drug based on the time sequence of drug administration and is unlikely to be attributed to concurrent disease or another source.

7.3. Procedure-Related Adverse Event

An adverse event that may be reasonably attributed to the procedure itself and not to the study drug. Other anesthesia or surgical techniques are more likely to have contributed to the occurrence of the adverse event.

7.4. Concomitant Medication-Related Adverse Event

An adverse event that may be more reasonably attributed to the use of another medication and not to the study drug.

7.5. Pre-Existing Condition-Related Adverse Event

An adverse event that may be more reasonably attributed to the existence of a pre-existing condition and not to the study drug. Pre-existing conditions with an increase in severity during the study will be evaluated to determine whether the study drug was likely responsible for the exacerbation.

The Investigator should assess all adverse events considered to be drug-related for potential reportability to the FDA.

The Investigator should follow all unresolved serious adverse events until their resolution, the patient is lost to follow-up, the patient has withdrawn consent or the adverse event is otherwise explained.

For purposes of this study, the following events are not considered adverse events, because they are expected to normally occur in conjunction with surgical procedures:

- Early postoperative pain (within 24 hours post-procedure)
- Chest or shoulder pain without associated ECG changes
- Hematocrit changes not to exceed a 30% change from baseline or requiring a blood transfusion
- Electrolyte imbalance without clinical sequelae, even if requiring correction
- Low grade temperature increase ($\leq 38.3^{\circ}\text{C}/\leq 101^{\circ}\text{F}$)
- Any pre-planned surgical procedures or interventions

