6.2.6. Postoperative Morbidity: Cystatin C will be drawn during pre-procedure and sent to external laboratory for analysis and calculation of the Cystatin C/Creatinine Ratio, to determine if the patient shows laboratory evidence of Sarcopenia. Postoperative lactate level will be drawn in the PACU as well as an arterial blood gas when an arterial line catheter is present. Overall postoperative morbidity will be recorded on POD 1, 3, 5 and 7 using the Postoperative Morbidity Survey assessed by chart review.

Morbidity type	Criteria
Pulmonary	De novo requirement for supplemental oxygen or other respiratory support (e.g., mechanical ventilation or CPAP)
Infectious	Currently on antibiotics or temperature $>38^{\circ}\text{C}$ in the last 24 h
Renal	Presence of oliguria ($<500\text{ mL/d}$), increased serum creatinine ($>30\%$ from preoperatively), or urinary catheter in place for a nonsurgical reason
Gastrointestinal	Unable to tolerate an enteral diet (either by mouth or via a feeding tube) for any reason, including nausea, vomiting, and abdominal distention
Cardiovascular	Diagnostic tests or therapy within the last 24 h for any of the following: de novo myocardial infarction or ischemia, hypotension (requiring pharmacological therapy or fluid therapy $>200\text{ mL/h}$), atrial or ventricular arrhythmias, or cardiogenic pulmonary edema
Neurological	Presence of a de novo focal deficit, coma, or confusion/delirium
Wound complication	Wound dehiscence requiring surgical exploration or drainage of pus from the operation wound with or without isolation of organisms
Hematological	Requirement for any of the following within the last 24 h: packed erythrocytes, platelets, fresh-frozen plasma, or cryoprecipitate
Pain	Surgical wound pain significant enough to require parenteral opioids or regional analgesia

CPAP = continuous positive airway pressure.

(Bennett-Guerrero, et al., 1999)

6.2.7. 30-Day Mortality and Readmission Rate: Patients will be contacted via phone 30 days after being discharged from the Hospital to collect mortality and readmission data. If research staff is not able to contact the patient, this data will be obtained from available medical records.

7. Adverse Events

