7.1. General

All adverse events (AE) and serious adverse events (SAE) from study drug administration until hospital discharge. An AE is defined as an undesirable clinical outcome regardless of whether it was directly caused by the study drug. An AE applies to any unintended event with an onset during the study or an exacerbation in the severity of a preexisting condition. All reported AEs will be recorded in the database with their respective description, date, actions taken, outcomes and assessment of the relationship with the study drug and protocol. AEs will be categorized using the Common Terminology Criteria for Adverse Events (CTACE) version 4.0. For the events not characterized by CTACE, the following definitions for severity will be applied:

Mild: Awareness of signs or symptoms, but easily tolerated; are of minor irritant type; causing no loss of time from normal activities; symptoms would not require medication or a medical evaluation; signs or symptoms are transient.

Moderate Interferes with the patient's usual activity and/or requires symptomatic treatment.

Severe: Symptom(s) causing severe discomfort and significant impact of the patient's usual activity and requires treatment.

A Serious Adverse Event (SAE) is defined as an event which leads to:

- Death due to any cause
- Life-threatening condition
- Results in persistent or significant disability/incapacity
- Requires in-patient hospitalization or prolonged hospitalization
- Necessitates an intervention to prevent a permanent impairment of a body function or permanent damage to a body structure
- Results in congenital abnormality

All SAE's will be reported.

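### The list of events exempt from adverse-event status in section 7.5 is ambiguous on transfusion, too broad on chest pain, and not reconciled with the serious-event rules

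*Combined protocol and SAP*

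**What the plan says.** All references are to the combined protocol and SAP.

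- **7.1** starts broadly: "An AE is defined as an undesirable clinical outcome regardless of whether it was directly caused by the study drug". Collection runs from study drug administration to hospital discharge. Serious events have their own definition, "A Serious Adverse Event (SAE) is defined as an event which leads to" one of several outcomes, among them "Requires in-patient hospitalization or prolonged hospitalization". The section ends: "All SAE's will be reported".
- **7.5** closes with a list of exemptions, introduced by: "For purposes of this study, the following events are not considered adverse events, because they are expected to normally occur in conjunction with surgical procedures". Two of the items are "Hematocrit changes not to exceed a 30% change from baseline or requiring a blood transfusion" and "Chest or shoulder pain without associated ECG changes". The item on early postoperative pain is limited to 24 hours; the chest and shoulder pain item has no such limit. Nothing in the list says what happens when a listed event is serious.
- **7.6** restricts AE collection to grades 3 and 4 that are at least possibly related, and keeps reporting of serious events whatever their attribution.
- **4.9** plans AE frequency tables and an evaluation of how AE type and severity relate to treatment.
- **6.2.6** records the Postoperative Morbidity Survey by chart review on postoperative days 1, 3, 5 and 7. Its hematological criterion is: "Requirement for any of the following within the last 24 h: packed erythrocytes, platelets, fresh-frozen plasma, or cryoprecipitate".

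**The concern.** An exemption list decides what can enter the safety comparison at all, so each item should give one answer for each patient and should give way when an event is serious. This list falls short in three places. The hematocrit item can be applied in two opposite ways to a transfused patient. The pain item places chest pain alongside shoulder pain with only an ECG condition attached, in a trial that schedules no ECG and enrols patients aged 65 or older. And the list and the serious-event rules can classify the same event differently, with no sentence saying which governs.

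At stake is the AE comparison in 4.9. Two staff members following the text could code the same patient differently, and an event of clinical weight could be absent from the tables without anyone departing from the protocol.

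**Working it through.** The plan gives no figure on this point: there is no expected transfusion rate, chest-pain rate or AE rate. The sample size calculation in 4.8 concerns shoulder pain and does not enter. The check is therefore a comparison of the rules.

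**Step 1. The hematocrit item.** It has two limbs, a change above 30% and a need for transfusion, and one negation.

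- Reading A: the negation governs both limbs. Exempt = not (above 30% or transfused).
- Reading B: the negation governs only the first limb. Exempt = (not above 30%) or (transfused).

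| Hematocrit change | Transfused | Reading A | Reading B |
|---|---|---|---|
| 30% or less | no | exempt | exempt |
| 30% or less | yes | AE | exempt |
| above 30% | no | AE | AE |
| above 30% | yes | AE | exempt |

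The readings agree for untransfused patients and disagree in both transfused rows. The ambiguity therefore falls entirely on the patients with the more consequential event.

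**Step 2. Transfusion in the other dataset.** The survey in 6.2.6 counts transfusion as hematological morbidity. Under reading B the same patient is morbidity in one dataset and no event in the other. The survey is only a partial backstop. Each assessment looks back 24 hours, so four assessments cover at most 4 × 24 = 96 of the 7 × 24 = 168 hours in seven days, or 96/168 = 57% of the time. That is coverage of time, not a share of transfusions.

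**Step 3. Chest pain in the other instruments.**

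- The PACU survey (6.2.4) asks about incisional, visceral and shoulder pain, and scores pain in general.
- The DASAIM score (6.2.5) grades pain at rest without a site.
- The Morbidity Survey's pain criterion concerns the surgical wound. Its cardiovascular criterion needs tests or treatment for named conditions such as infarction or ischemia.

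None of these identifies chest pain as such. The word ECG appears only in the 7.5 item, so the plan does not say how the condition is judged when no tracing was taken.

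**Step 4. The list against the serious-event rules.** Take chest pain without ECG changes that prolongs the stay. Under 7.1 it is serious and must be reported. Under 7.5 it is not an AE. Section 7.6 repeats the reporting duty but does not mention the list. Section 4.9 tabulates AEs and does not say that reported serious events enter the tables regardless of 7.5. Reporting is secured; entry into the comparison is not.

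**Step 5. What the list can remove beyond 7.6.** A non-serious event that is grade 1 or 2, or judged unrelated, is already outside collection. The list can change the result for grade 3 or 4 events that are at least possibly related, and for serious events.

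**Step 6. Scale per patient.** Enrolment is 100 at 1:1, so 100/2 = 50 per arm. Each patient coded the other way moves that arm's AE proportion by 1/50 = 2 percentage points. How many patients that would be cannot be derived from the documents.

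**The case against.** The strongest reply is that the list, read sensibly, does little harm.

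- **Reading A is the more plausible.** The lead-in confines the list to what normally accompanies surgery. The electrolyte item says outright that treated cases stay exempt, and the hematocrit item has no such words. Reading B also yields the odd result that an untransfused 31% fall is an AE while a transfused 40% fall is not. This stands. A reader might infer that every transfused patient is exempt, and the text does not establish that. It does permit it grammatically, so the item still needs rewording.
- **Serious events are protected.** Section 7.1 builds the serious definition on an event, not on a non-exempt AE, and 7.1 and 7.6 require all of them to be reported. This stands for reporting. It does not settle whether they enter the 4.9 comparison.
- **Section 7.6 already drops most non-serious events**, and surgical bleeding may be classed as procedure-related under 7.3. This stands and limits the effect; it does not reach severe, possibly related events.
- **The ECG condition may presuppose that an ECG was done.** That is possible, and the text does not say that untested patients are exempt by default. It does not say the opposite either. The exemption covers the symptom only: ischemia, arrhythmia and pulmonary edema are not listed and fall under the Morbidity Survey.
- **Collection ends at discharge**, so the chest-pain exemption is not open-ended. This stands.
- **The blood-loss figures in the Background** (20.2 against 60 mL, lower with deep blockade, in colorectal surgery) say nothing about transfusion and do not suggest that a harm of deep blockade is being concealed. This stands; the point does not rest on them.

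**Conclusion.** The point holds as a drafting defect that should be corrected. The hematocrit item supports two readings that differ for every transfused patient. The pain item exempts chest pain of any severity or cause within the collection window if there are no associated ECG changes. The list and the serious-event rules are not reconciled.

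A reader might go further and infer that real or serious harms are lost from the trial. The documents do not support that: serious events must be reported, transfusion is partly captured by the Morbidity Survey, and Survey measures are collected for analysis under 4.9. What can be lost is an event's place in the AE tables, mainly severe and possibly related chest pain, transfused hematocrit changes under one of two readings, and listed events that turn serious.

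The number of affected patients cannot be estimated, because the documents give no rate for either event. The conclusion assumes only that site staff apply 7.5 as written. The primary endpoint is unaffected.

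**What to change.** Make three changes in 7.5:

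1. Replace the hematocrit item with: *Hematocrit changes of 30% or less from baseline that do not require a blood transfusion.*
2. Limit the pain item to shoulder pain, which the PACU survey already records for the primary endpoint, and remove chest pain from the list.
3. Add: *None of these exemptions applies to an event that meets a serious criterion in 7.1.* This reconciles 7.5 with 7.1 and 7.6. Any such event then counts as an AE and belongs in the 4.9 comparison.

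No new procedure or visit is needed. The cost is the approval step that 8.3 requires for protocol changes and a few more AE entries.

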7.6. Reporting of Serious and Non-Serious Adverse Events

Sugammadex is FDA-approved for the reversal of steroidal neuromuscular blocking drugs and the potential risks are well-documented. We will only collect adverse events that rise to the level of grades 3 and 4 with an attribution of possible, probable, or definitely related to the device. Serious Adverse Events, regardless of attribution, will be reported per MDACC's standard practice and requirements, and per sponsor guidelines.

8. Ethical considerations

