4.7. Blinding, Allocation and Concealment

Patients and TOF-watch assessors will be blinded to the study drug. The assessor of the primary outcome will not be involved in randomization, or allowed in the operating room during surgery. Anesthesiologists will not be blinded to study drug but he/she will be blinded to the TOF watch response. The surgeon and PACU staff will be blinded to the group assignment.

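### Sections 7.1 and 7.6 give incompatible collection rules for non-serious adverse events, and section 4.9 compares adverse events by arm without saying which set it uses

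*Combined protocol and SAP*

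**What the plan says.** Section 7.1 is broad. It states that "An AE is defined as an undesirable clinical outcome regardless of whether it was directly caused by the study drug". It then says "All reported AEs will be recorded in the database with their respective description, date, actions taken, outcomes and assessment of the relationship", and that sentence goes on to name both the study drug and the protocol as the things to which the relationship is assessed. Grading is by CTCAE version 4.0, with a fallback: "For the events not characterized by CTACE, the following definitions for severity will be applied". The fallback levels are mild, moderate and severe.

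Section 7.1 describes timing in two ways. It opens with "All adverse events (AE) and serious adverse events (SAE) from study drug administration until hospital discharge", a sentence without a verb, and later says that an adverse event is any unintended event beginning while the study is under way.

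Section 7.6 is narrow. It notes that Sugammadex is approved and its risks are well documented, then restricts collection to "adverse events that rise to the level of grades 3 and 4 with an attribution of possible, probable, or definitely related to the device". Serious events are exempt: "Serious Adverse Events, regardless of attribution, will be reported".

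Section 7.2 makes drug-relatedness a matter decided "in the judgment of the Investigator". Section 4.7 says "Anesthesiologists will not be blinded to study drug", while the patients, the surgeon and the PACU staff are blinded.

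Section 4.9 plans frequency tables of adverse events and an evaluation of their type and severity against treatment. It names no grade range, attribution limit or source section.

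**The concern.** For a non-serious event, staff cannot follow both rules: one has them record it whatever its grade or cause, the other has them leave out most such events. Section 4.9 then tests whatever was entered, so the content of the by-arm safety comparison depends on which section the site follows.

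Two consequences follow if 7.6 is the working rule. First, the severity comparison in 4.9 is confined, for non-serious events, to grades 3 and 4, and nothing says how that cut applies to events scored mild, moderate or severe outside CTCAE. Second, relatedness becomes a condition of entry. A judgement that may be made with knowledge of the arm would settle which events exist in the data, and an event filtered out at that stage cannot be recovered by a sensitivity analysis.

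**Working it through.** The plan states no figure to reproduce here, so the check sets the two rules against each other. Take non-serious events that are not on the list of six event types which section 7.5 says are not adverse events. Split them by grade and by attribution, reading device as the study drugs:

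| Non-serious event | Under 7.1 | Under 7.6 |
|---|---|---|
| Grade 1-2, at least possibly related | in | out |
| Grade 1-2, judged unrelated | in | out |
| Grade 3-4, at least possibly related | in | in |
| Grade 3-4, judged unrelated | in | out |

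The rules agree in 1 of the 4 cells and differ in 3. Serious events are reported under both.

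The word device changes the one agreeing cell:

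- **Read literally.** No device is a randomized treatment, so almost no non-serious event qualifies under 7.6.
- **Read as the study drugs.** This is the most plausible sense. Section 9.3 also refers to device shipments and device effects, which suggests leftover wording, and sections 5 and 8.6 identify the study drugs as Sugammadex and Neostigmine. The table above applies.
- **Read as Sugammadex alone**, the only drug named in the rationale of 7.6. The filter could not then work alike in the neostigmine arm.

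Next, does any other text say which rule prevails?

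- No section says that 7.6 overrides 7.1.
- Mild and moderate definitions in 7.1 have little use for non-serious events if only grades 3 and 4 are kept.
- Sections 7.3 to 7.5 classify events due to the procedure, other medication or a pre-existing condition rather than the study drug. Under 7.6 the non-serious ones would largely never be collected.
- Section 7.5 asks the Investigator to consider every drug-related event for possible FDA reporting, with no grade limit.
- The possible, probable and definite scale in 7.6 does not match the source categories in 7.2 to 7.5.
- Section 8.8 requires any adverse event to appear in the medical record, without a grade or attribution limit.

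Finally, the set for 4.9. It could be everything in the table, one cell of it, or nearly nothing, depending on the section followed and the meaning given to device. Section 4.9 also does not say whether serious events that fail the 7.6 filter enter its tables. The documents give no adverse event rate, so the size of the difference cannot be calculated, and none is assumed here.

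**The case against.** The best defence is that 7.6 is the specific rule and 7.1 the general one. Section 7.1 is headed General, its opening sentence is incomplete, and its database rule covers only reported events, which could mean those that pass 7.6. Section 7.6 is explicit, and 4.9 can tabulate only what was collected. Restricting non-serious collection for an approved drug is a choice for which 7.6 gives a reason, and device is a slip that most readers would correct for themselves.

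Part of this stands. The sponsor may well have meant 7.6 to govern, and a grade threshold is a legitimate economy. But the narrowing reading rests on inference, and the text listed in the working fits it poorly. Accepting it settles which set is used, yet the relatedness filter and the missing link to the mild, moderate and severe scale remain.

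The defence is also right that bias is not shown. The surgeon and PACU staff are blinded, and no section says that an unblinded anesthesiologist attributes events. What can be said is that 7.2 gives the judgement to the Investigator and that the Investigator's blinding is not stated.

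A reader might go further and infer that collection starts only when the reversal agent is given at the end of surgery, so that events during the randomized block are lost. The documents do not support that. Section 7.1 also covers events beginning during the study and has relationship assessed to the protocol as well as the drug, which leaves room for attribution to block depth. Section 8.6 does not list rocuronium with the study drugs, but it is a section on costs and a thin basis for defining the safety window. The two timing statements need aligning; they do not show a gap.

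**Conclusion.** The inconsistency is real and should be corrected. It concerns non-serious events only: three of the four grade-by-attribution groups are in under 7.1 and out under 7.6, and 4.9 does not choose. If 7.6 governs, the by-arm comparison of those events is pre-filtered on a judgement that may not be blinded. That rests on reading device as the study drugs of both arms; the other readings are worse.

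The reach is modest. Adverse event counts are neither a primary nor a secondary outcome. The Postoperative Morbidity Survey, DASAIM scores, nausea and vomiting, 30-day mortality and readmission carry no such filter. It would be wrong to infer that serious events go unreported, that the trial lacks safety data, or that a bias between arms has been demonstrated.

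**What to change.** Reconcile 7.1, 7.6 and 4.9 into one collection rule applied identically in both arms:

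- Replace device in 7.6 with the randomized treatments of both arms, that is, block depth together with its reversal agent.
- If a threshold is kept, base it on grade and say how it maps to events scored mild, moderate or severe.
- Record relatedness as a variable for each event, not as a condition of entry, and say whether the person assigning it knows the arm.
- Have 4.9 name the set it tabulates and state that all serious events are in it.
- Align the two timing statements in 7.1 so that the window clearly includes the period of randomized block.

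The exclusions in 7.5 and the reporting of all serious events can stay as they are. The cost is amended wording and modestly more event entry and grading for 100 patients. Section 8.8 already requires the occurrence and status of any adverse event in the medical record, so the added work is mainly grade and relatedness for events that 7.6 now leaves out.
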